3.8.4.2 Feasibility Endpoints

Analysis of feasibility endpoints will use descriptive statistics to characterize the variability of uptake of FIs across types of testing venues.

3.9 Human Subjects/Ethical Considerations

The Linkage-to-Care component of the study involves a randomized intervention using FIs to link HIV-positive individuals to HIV care after diagnosis. This component is public health research. In this component, HIV test sites will be randomized, not individuals, and no de novo individual-level data will be collected. Instead, (de-identified) HIV surveillance data routinely collected by the Departments of Health (DOH) in the two communities will be analyzed. Because this research involves minimal risk and would be impracticable with informed consent, a waiver of patient informed consent will be requested under 45 CFR 46.116 (c) or (d).

The protocol will be submitted to appropriate IRBs (a central and/or local site IRBs) for ethical review prior to study initiation. Any subsequent modifications to the protocol will be submitted to appropriate IRBs, and, at a minimum, the protocol will be submitted annually for continuing review and approval by these same ethics boards.

This component of the study involves an intervention using FIs to link HIV-positive individuals to HIV care after diagnosis. These incentives are described in detail in the intervention section for this study component. No additional incentives (for example for transportation) will be given to individuals who participate in this component of the study.

No individual data, other than what exists in the surveillance databases, will be collected from study participants in the Linkage-to-Care component of this study. To assess the impact of the study on Linkage-to-Care in the communities of Washington, D.C. and the Bronx, HIV surveillance data routinely collected by the DOH will be analyzed. Data from the DOHs will be provided to the study team in a de-identified fashion, as per usual HIV surveillance procedures.

No study-specific laboratory testing will be conducted under this protocol. Therefore, no additional study-related test results will need to be reported to authorities. HIV testing and care data collected during routine clinical care will be reported per local HIV and AIDS reporting requirements.

3.10 Safety Monitoring and Adverse Event Reporting

The study team will not collect or report Adverse Events because there is no biomedical intervention. However, the team will collect and report all social harms that are brought to the attention of study staff members, using a study-specific incident report form. This form will be anonymous and will query common social harms such as altered personal relationships, forced change in housing, and physical violence. The form will also include space for a written narrative to document additional details of any social harm experienced. All research staff will be trained to properly complete the form. As a part of study training, research staff will also be trained on the provision of referrals to counseling and social service support. Reports of social harms will be reviewed quarterly or more often, if indicated, and reported to the medical officer together with any actions that are taken. Social harms will be summarized and reported to appropriate IRB(s) on an annual basis.

4.0 VIRAL SUPPRESSION

4.1 Study Objectives for Viral Suppression

The **primary feasibility objectives** for using FIs to incentivize HIV-positive patients to achieve and maintain viral suppression (HIV RNA < 400 copies/mL) will be measured by determining the following:

- Proportion and number of patients in care, on ART (eligible for incentives), and receiving incentives upon achieving VL suppression
- Number of incentives disbursed compared with the total number of incentives available to eligible patients over the study duration [measurement of duration of viral suppression]
- Overall cost of program including staffing, infrastructure and incentives
- Number of patients previously adherent to ART who change from non-intervention to intervention care sites

In order to monitor the implementation of the FI program, certain parameters will be gathered from a subset of participating sites at various time points to ensure program quality. These parameters will include: the proportion and number of patients in care, on ART (eligible for incentives) and receiving incentives, as well as the incentive amount received compared with the total number on ART who would be eligible.

The **primary effectiveness objective** is to compare an FI intervention with the SOC for achieving and maintaining suppressed VL in HIV-positive patients in care, managed under the prevailing guidelines for the initiation of ART. For sites in each intervention arm, this objective will be measured by the following:

- Comparing the mean proportion of patients in care at a site who have suppressed VL (HIV RNA <400 copies/mL) during the fixed 12-month calendar evaluation period beginning 12 months after initiation of the FIs at that site
- Comparing the trend in mean proportion of patients in care at a site who have suppressed VL over time since initiation of FIs

• Comparing the mean proportion of patients who have suppressed VL (HIV RNA <400 copies/mL) after cessation of incentives

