3.6.2 Procedures at Care Sites

Participating HIV care sites will serve as the comprehensive 'medical home' for coordination of all HIV-positive patient care needs, including substance use, mental health, and other support services.

As newly diagnosed HIV-positive patients present for care, care sites will evaluate CD4 cell count and VL. Care sites will then create an appropriate medical plan for each patient, consistent with current HIV care and treatment guidelines. Simultaneously, care

sites will also assess patients and link them as appropriate to support services. Finally, valid coupons distributed by HIV test sites will be redeemed with FI gift cards.

Prior to study implementation, all HIV care site staff will be trained on the procedures for the FI intervention, ART initiation according to current guidelines, and the importance of linking HIV-positive patients to appropriate support services. In addition, as part of study orientation and training for HIV care providers, existing support service linkages will be reviewed.

To collect clinic-level information on services available to patients in the two jurisdictions, HIV care sites will be surveyed at baseline and annually thereafter to ascertain support services available on- and off-site (e.g., social services, substance use treatment, support groups, mental health resources, etc). The study team will develop and maintain a comprehensive list of support services in the two intervention communities. In addition, the study will regularly update lists for care sites of contact persons and referral processes at support service agencies.

Because the study will use surveillance data to measure outcomes and will not collect data on individual patients, the study will not be able to document or track linkages to ancillary services in the Linkage-to-care and Viral Suppression study components. Information on referrals made and completed by patients is not part of the surveillance data that will be analyzed for study outcomes. Likewise, offering FIs for completion of linkages to drug treatment or mental health services is not possible, as it would also require following individual patients with explicit data collection. However, for the subset of patients completing Patient Survey, we will collect data on the frequency of use, ease of access, and patient experiences with support services (including mental health, drug abuse, case management, etc).

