4.5 Intervention for Viral Suppression

HIV-positive individuals at HIV care sites assigned to the FI intervention will receive FIs (gift cards worth \$70) to reinforce adherence to ART as measured by confirmation of each suppressed VL measurement (<400 copies/mL). The gift cards will be distributed at the HIV Care sites during each routine, quarterly clinic visit that a study participant demonstrates a suppressed VL.

In the event participants report full adherence to their providers but have not succeeded in achieving VL suppression, providers will be expected to obtain resistance testing, as recommended by current treatment guidelines, and to alter their patients' regimens accordingly. Once patients with resistant HIV are on appropriate regimens, they will again be eligible for FIs for viral suppression. The specific procedures for HIV care sites to distribute the FIs for viral suppression will be outlined in the HPTN 065 SSP.

This intervention will be compared to SOC support for ART adherence through the use of routinely collected HIV surveillance data.

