4.6.1 Monitoring HIV Care Sites

It is possible that members of the intervention communities, particularly those who are HIV-positive, will learn of the FI intervention to promote viral suppression and seek out HIV care sites offering these incentives. In an effort to minimize significant migration of patients from HIV care sites without FIs to ones that offer them, the following rules have been put into place:

- A patient must have at least one VL measurement at the HIV care site between three and nine months prior to the first suppressed VL for which he or she may receive an incentive. Both of these VL measurements must be done at the same HIV care site.
- All subsequent VL measurements for which a patient may receive FIs must be performed at the same HIV care site.

If a patient changes HIV care sites during the course of the study, he or she will be required to "establish care" at the new HIV care site prior to receiving any FI for a suppressed VL as indicated above. Specifically, to receive an FI again, the individual must have a VL measurement at the new HIV care site and return in three to nine months for a repeat VL measurement. The results of the second test will determine whether the person receives the FI or not.

Despite this barrier to HIV-care-site migration, the FI intervention may encourage this phenomenon; thus, the study team will use surveillance data to monitor the case load at each site at frequent intervals. By monitoring HIV care site case load over time, the team will be able to determine if significant migration is taking place. This will motivate discussions with the community advisory group to design other mechanisms to minimize such migration or if needed a redesign of this component of the study may be embarked on by the study team.

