4.8 Statistics and Data Analysis for Viral Suppression

4.8.1 Endpoints

4.8.1.1 Endpoints for the feasibility of using financial incentives in the HIV-positive population for viral suppression

The feasibility endpoints for the viral suppression component of the study will include the following:

- Number of individuals eligible for incentives and receiving incentives at a select subset of sites for select time points
- Cost of program including staffing, infrastructure and incentives

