4.9 Human Subjects/Ethical Considerations

The Viral Suppression component of the study involves an intervention using FIs to encourage HIV-positive individuals on ART to be adherent to their medications and to maintain HIV VL suppression. This component is public health research. In this component, HIV care sites will be randomized, not individuals, and no de novo individual-level data will be collected. Instead, (de-identified) HIV surveillance data routinely collected by the DOH in the two communities will be analyzed. Because this research involves minimal risk and would be impracticable with informed consent, a waiver of patient informed consent will be requested under 45 CFR 46.116 (c) or (d).

The protocol will be submitted to appropriate IRBs (a central and/or local site IRBs) for ethical review prior to study initiation. Any subsequent modifications to the protocol will be submitted to appropriate IRBs, and, at a minimum, the protocol will be submitted annually for continuing review and approval by these same ethics boards.

No individual data, other than what exists in the surveillance databases, will be collected from study participants in the viral suppression component of this study. To assess the impact of the study on viral suppression in the communities of Washington, D.C. and the Bronx, surveillance data routinely collected by the DOHs will be analyzed. Data from the DOHs will be provided to the study team in a de-identified fashion, as per usual HIV surveillance procedures.

No study-specific laboratory testing will be conducted under this protocol. Therefore, no additional study-related test results will need to be reported to authorities. HIV testing and care data collected during routine clinical care will be reported per local HIV and AIDS reporting requirements.

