7.2 HIV Surveillance Data

The CDC's national system for the surveillance of HIV infection is based on mandatory name-based reporting of all HIV and AIDS cases in every state and Washington, D.C. Health departments maintain case records of every new and established HIV case according to the HIV case definition. Laboratory reports of positive HIV test results and provider reports of new confirmed diagnoses are tracked by the health departments. In most jurisdictions, data from mandatory reporting of CD4 cell count and VL from all laboratories are linked via case names to individuals maintained in the eHARS data entry and reporting system (not all states have mandatory reporting of all VL and CD4 cell count). Across the United States, and within each community, the system captures key variables for this study. The key data elements from HIV surveillance that will be used are listed in Table 6.

Key Data Elements	Primary Use	
CD4 result CD4 date VL result VL date Name of facility of diagnosis	Primary Use Study intervention outcome measures	

 Table 6.
 Key Date Elements and Primary Use

Key Data Elements	Primary Use	
Date of birth (DOB)		
Race/ethnicity	Stratification variables	
Transmission category	Stratification variables	
Sex at birth		
Date of death		
Cause of death	Additional outcome measures	
Previous negative test, lab based		
Previous negative test, self-reported		
Place of residence at diagnosis	Adjustment variables	
Current place of residence	Aujustitient variables	
Source of report		
Surveillance method	Variables for data quality control	
Duplicate		

De-duplication (removing double-reported cases) of cases between jurisdictions occurs at least annually, with case tracing on an ongoing basis as individuals relocate and new diagnostic labs are investigated in a new jurisdiction. Cases are identified through active follow-up of positive Enzyme Immunoassay (EIA), positive WB and detectable VL reports from names not matched in the local eHARS database, as well as through reporting by providers. Communities selected for this study (both intervention and non-intervention communities) have quality data collected on these parameters.

HIV surveillance data can describe treatment success based on reported VL measurements. However, specific information on type of treatment received is not collected.

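### The Section 4.1 migration measure is a one-way raw count in an undefined group with no comparator, so alone it cannot separate incentive-driven moves from ordinary changes of clinic

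*Protocol*

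**What the plan says.** Section 4.1 gives four primary feasibility measures for the viral suppression component. The last is the "Number of patients previously adherent to ART who change from non-intervention to intervention care sites". The section does not define previous adherence, and it states no denominator, no count in the opposite direction and no pre-study rate.

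On the data, Section 7.2 says that in HIV surveillance "specific information on type of treatment received is not collected", and Section 4.9 says that "No individual data, other than what exists in the surveillance databases, will be collected from study participants in the viral suppression component". Section 4.5, however, describes the gift cards as given "to reinforce adherence to ART as measured by confirmation of each suppressed VL measurement", so the protocol already treats a suppressed viral load (VL) as its measure of adherence. Table 5 in Section 7.1 lists treatment site, VL date and VL result among the surveillance variables.

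The feasibility endpoints in Section 4.8.1.1 are the "Number of individuals eligible for incentives and receiving incentives at a select subset of sites for select time points" and the cost of the program. Migration is not among them. The feasibility analysis in Section 4.8.4.2 covers uptake and cost only.

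**The concern.** Patients change clinic for many reasons, and the protocol itself expects some to do so (Sections 4.6.1 and 4.7). When half the study clinics in a city pay incentives, a fair share of ordinary moves out of SOC clinics will end at a paying clinic. A count of those moves is therefore above zero with no incentive effect at all, and nothing in the stated measure shows how far above zero it has to be before it means anything.

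Section 1.2 says the study is to guide the design and anticipate the costs of a later community trial, and Section 4.6.1 treats significant migration as a possible ground for redesigning the component. Whether payment draws already-suppressed patients to paying clinics bears on both. The measure chosen to answer that question cannot do so alone, and it does not appear in the endpoint list that is meant to carry it out.

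**Working it through.** The protocol states no migration rate, threshold or expected count, so there is no figure of its own to reproduce. The calculation below is an illustration of what the count would show when the incentive has no effect.

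**Inputs from the protocol**
- Clinics: 10 FI and 10 SOC per city (Section 4.4). A patient leaving an SOC clinic for another study clinic in the city has 19 possible destinations, of which 10 are FI.
- Patients at the top 20 sites: about 5,000 in Washington, D.C. and 16,000 in the Bronx, 21,000 in all (Section 4.8.2).
- Suppression in 2008 among patients with a VL assessed: 57% of 8,316 in the Bronx and 67% of 2,926 in D.C. (Section 4.8.2).
- SOC suppression in Table 3: 60%.
- FI period: 24 months (Section 4.7).

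**Assumptions not in the protocol**
- A yearly rate *r* of ordinary change between study clinics of 3%, 5% or 10%, the same in both arms.
- Patients split equally between arms.
- All other clinics in the city equally likely as the destination.

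**Suppressed patients in SOC clinics**
- Base A, patients with a VL assessed: 0.57 × 8,316 + 0.67 × 2,926 = 4,740 + 1,960 = about 6,700; half is about 3,350.
- Base B, all patients: 21,000 / 2 × 0.60 = 6,300.

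**Expected SOC-to-FI moves over 24 months with no incentive effect**

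Count = base × [1 − (1 − r)²] × 10/19

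| r per year | 1 − (1 − r)² | × 10/19 | Base A (3,350) | Base B (6,300) |
|---|---|---|---|---|
| 3% | 0.0591 | 0.0311 | 104 | 196 |
| 5% | 0.0975 | 0.0513 | 172 | 323 |
| 10% | 0.1900 | 0.1000 | 335 | 630 |

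Under the same assumptions the FI-to-SOC count has the same expectation, so the net flow is zero. The one-way count runs from about 100 to 630 while the two-way difference correctly shows nothing. Base A is the safer of the two, because the suppression percentages in Section 4.8.2 were observed in patients with a VL assessed; Base B extends a similar percentage to everyone in care.

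**Do other provisions supply the missing comparator?**
- Section 4.6.1: "the study team will use surveillance data to monitor the case load at each site at frequent intervals". Case load reflects new patients, deaths and moves away as well as transfers. It does not show who moved or whether they were suppressed.
- Section 4.8.1.2 follows patients with VLs at several providers, and Section 4.8.4.1 plans a sensitivity analysis for those who switch. Both protect the effectiveness estimate.
- Section 8.3 puts migration by assignment under study monitoring but names no measure or benchmark.

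None of these gives the Section 4.1 count anything to be set against.

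**The case against.** There are four objections of substance.

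*The measure can be computed.* A reader might infer from Sections 7.2 and 4.9 that, since neither treatment nor adherence is recorded, the count is impossible. The documents do not support that. Section 4.5 uses suppressed VL as the measure of adherence, and VL date, VL result and treatment site are in surveillance. A patient suppressed at an SOC clinic whose later VLs are at an FI clinic can be identified. What stands is narrower: the group is not defined, and adherence is seen only by proxy.

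*Nobody says the count will be blamed on the incentive.* A reader might infer that ordinary moves would be reported as incentive-driven migration. No section says so. What stands is that the count alone gives no means of telling the two apart.

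*One direction is enough for cost.* An already-suppressed patient arriving at a paying clinic costs money whatever the motive. That is fair, and it is a reason to keep the count as a numerator. But a patient who leaves an FI clinic also ends a stream of payments, so the net flow matters for cost too.

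*The detail belongs in the statistical analysis plan, and switching is followed elsewhere.* Section 4.8.1.2 does leave to that plan the handling of patients treated at more than one site. But the direction and form of this measure are already set in the protocol's objectives, and the other provisions serve operations or the effectiveness analysis.

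The size is also open to challenge. The switching rates are assumed, and clinic sizes are very uneven (50 to 3,300 patients in the Bronx, 35 to 1,400 in D.C.), so equal destinations are a simplification. This affects the figures and not the structural point.

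**Conclusion.** The point holds in a limited form. As fixed in Section 4.1, the measure is a one-way raw count in an undefined group, without denominator, reverse flow or background rate, and Section 4.8.1.1 does not list it. Alone it cannot distinguish incentive-driven moves from ordinary ones. With no incentive effect it would be about 100 to 335 patients (base: VL assessed in 2008) or about 200 to 630 (base: all 21,000) over 24 months, if 3% to 10% a year change study clinic. Those rates, equal switching in both arms, an even split of patients and equal destinations are assumptions.

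The consequence is confined to what the study can conclude about migration. Section 4.8.4.1 assigns patients to the care site held at trial onset and plans a sensitivity analysis for switchers, so the primary effectiveness analysis is unaffected. This is a worthwhile, cheap improvement to a descriptive measure and not a threat to the main result.

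**What to change.** Replace the Section 4.1 bullet and add the matching endpoint to Section 4.8.1.1:
- **Group:** patients whose last VL before FI onset was <400 copies/mL at a study clinic, stated as the proxy for previous adherence.
- **Measure:** the percentage with later VLs at a clinic of the other arm, SOC to FI and FI to SOC side by side, each with its numerator and denominator.
- **Background:** where the surveillance data allow, the same two percentages for the pre-study year.
- **Reading:** judge migration from the net excess of SOC-to-FI over FI-to-SOC moves, against the pre-study difference where available.

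The cost is a wording change and one more descriptive table. It draws on the dated VL results and ordering sites that the primary analysis already needs, so no new data are collected. The drawback is that suppression stands in for adherence.
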